7.7 EFFICACY ENDPOINTS AND ANALYSIS

All the efficacy tables will be run for Safety Set for Phase 1 and for Phase 2a. Where specified additionally, sensitivity analyses on DDS will be run.

In addition, a sensitivity analysis on ORR (as defined by RECIST by investigator and the independent assessor) will be performed for all patients in the safety set for patients receiving at least one full planned dose.

7.7.1 ANALYSIS OF PRIMARY ENDPOINT

Phase 1 (Dose Escalation)

DLT is defined as an AE or abnormal laboratory value assessed as unrelated to underlying disease, disease progression, inter-current illness, or concomitant medications, that occurs ≤ 28 days following the first dose of AFM24 (Cycle 1) and that meets any of the following criteria shown in Table 1. The CRF record of DLT will be used to determine the DLT. Clinically relevant toxicities will be evaluated according to the National Cancer Institute (NCI)/National Institutes of Health (NIH) Common Terminology Criteria for Adverse Events (CTCAE) v5.0. Patients who experience a DLT during Cycle 1 must permanently discontinue AFM24.

Patients must receive $\geq 80\%$ of their assigned AFM24 dose in Cycle 1 and complete the 28-day DLT observation period or have had a DLT within the first cycle of treatment to be considered evaluable for DLT. The exact definition of the DLT is given in Section 3.4.2 of the Protocol.

A 2-parameter BLRM (Neuenschwander et al., 2008) will be used for dose escalation of the monotherapy. The model will be run in house by Affimed. Detailed description of the process can be found in the Protocol.

The model is formulated as follows:

$$\text{logit}(p(d)) = \log(\alpha) + \beta * \log(d/d^*)$$

where $\text{logit}(p) = \log(p/(1-p))$. $p(d)$ represents the probability of having a DLT in the first cycle at dose d , $d^* = 180$ mg is the reference dose, allowing for the interpretation of α as the odds of a

[figure not shown]
CONFIDENTIAL

Page 14 of 22

Statistical Analysis Plan template version 1.0 dated 27-MAR-2019

DLT at dose d^* , and $\theta = (\log(\alpha), \log(\beta))$ with $\alpha, \beta > 0$ is the parameter vector of the model.

Non-clinical data have been used to determine an informative prior distribution for θ . The details for the calculation can be found in the Protocol section 9.3.4.2. The resulting distribution is as follows:

The analysis of the primary endpoint will be done on DDS. Number and percentage of the DLTs for every dose level will be summarized, together with the predicted DLT probability and predicted probability of overdosing. The analysis will be repeated on the updated data before each SRC. Final results obtained from complete data from Phase 1 will be reported in the CSR.

Listing of all the DLTs will be created as a part of AE listings and separately.

Phase 2a (Dose Expansion)

Primary endpoint for this phase will be Overall response rate (complete response [CR] + partial response [PR]) assessed by local RECIST v1.1. Best confirmed overall response will be used to define the ORR. The table below summarizes the confirmation rules:

Response at first visit	Response at consecutive visit (at least 4 weeks after the initial assessment)	Confirmed Response at visit
CR	CR	CR
CR	PR	PD
CR	SD	SD*
CR	PD	PD
PR	CR	PR
PR	PR	PR
PR	SD	SD*
PR	PD	PD
SD	CR	SD*

CONFIDENTIAL

Page 15 of 22

Statistical Analysis Plan template version 1.0 dated 27-MAR-2019

SD	PR	SD*
SD	SD	SD*
SD	PD	PD

CR = complete response; PD = progressive disease; PR = partial response; SD = stable disease

* - In order to assign Stable Disease as a confirmed response, there has to be another assessment of at least SD no less than 7 weeks after the initial visit. If this criterion is not satisfied, assign PD.

If the closest consecutive visit is closer than 4 weeks, or is not evaluable, use the next available assessment for confirmation. The last visit has no confirmed response. For iRECIST data similar approach will be used to define the confirmed response at visit.

Simon's two-stage design will be used to determine the outcome of the study in each of the three cohorts. The table below shows the decision thresholds for the design for all three cohorts:

Indication	Interim Analysis		Final Analysis	
	Number of subjects	OR, that may lead to stop	Number of subjects*	OR (rejection of the null hypothesis)
RAS-wt, microsatellite stable CRC	11	≤1	39	≥4
ccRCC	15	≤2	41	≥10
NSCLC EGFRmut	15	≤2	41	≥10

CRC = colorectal cancer; EGFRmut = epidermal growth factor receptor mutant; RAS-wt = rat sarcoma genes-wild type; NSCLC = non-small cell lung cancer; OR = objective response

*Up to a total of N~40 subjects per Cohort

The final analysis will take place after the last expansion arm was closed for futility or the last patient of the last expansion arm had the final end-of-study visit. Summaries will include the count and percentages of different best confirmed overall responses for each cancer type and observed ORR. In the final analysis, a p-value using the exact binomial test will be calculated comparing the response proportion to the probability stated under H_0 for each indication separately.

Listing of CT scan data, reporting both confirmed and unconfirmed responses at all visits will be created. Additionally, biopsy data will be listed.

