4.3 Subject Withdrawal from Study

Throughout the study, treatment with AFM24 may continue until the occurrence of 1 of the following events, whichever comes first:

- Subject withdrawal of consent;
- Disease progression (if initial radiological progressive disease is observed, while the clinical condition of the subject is stable, treatment continuation is allowed at the discretion of the Investigator. If treatment is continued after initial progressive disease, a confirmatory scan should be acquired within 4 to 6 weeks);
- Occurrence of intolerable toxicity;
- DLT during Cycle 1 in the Phase 1 part;
- Subject non-compliance and the need for withdrawal for this reason as assessed by the Investigator; or
- Investigator decision that it is in the subject's best interest to withdraw from the study.

Upon withdrawal from study drug, the reason for withdrawal should be sought and recorded in the subject file and the withdrawal will be captured in the electronic case report form (eCRF). Every effort will be made to complete the End of Treatment visit, the Safety Follow-up visit and for the subject to be followed up every 3 months thereafter. Where a subject withdraws his/her consent to participate in the study, such follow-up assessments cannot be conducted. The management and holding of data around subject withdrawal will be described in the subject ICF.

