7.2.11 Disease Response Assessment

Disease response will be assessed by the Investigator, using local RECIST v1.1 (Eisenhauer et al., 2009; Schwartz et al., 2016) and Response Evaluation Criteria in Solid Tumors for immunotherapy (iRECIST) (Seymour et al., 2017). In Phase 1 and 2a, imaging results will also be sent for independent central review. Tumor assessment with CT and/or MRI will occur at Screening as well as at timepoints specified in the SoA tables (APPENDIX A [Section 14.1] for weekly dosing schedule and APPENDIX B [Section 14.2] for q2w dosing schedule). Partial or complete response needs to be confirmed with repeated assessment at least 4 weeks after the initial assessment.

If initial radiological progressive disease is observed, while the clinical condition of the subject is stable, treatment continuation is allowed at the discretion of the Investigator. If treatment is continued after initial progressive disease, a confirmatory scan should be acquired within 4 to 6 weeks. However, the first successive scheduled timepoint after the confirmatory scan may be skipped if the window is considered not clinically relevant (up to the discretion of the Investigator).

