9.3.8.2 Phase 2a (Dose Expansion)

An IA will be performed for each cohort independently, once the defined number of subjects (11, 15, and 15 subjects for Cohorts A, B, and C, respectively, – see [Table 10](#)) in the respective cohort have completed their first post-baseline assessment and its confirmation (2nd post-baseline assessment, ie, ≥ 12 weeks post-baseline) to be categorized under the primary response endpoint or have withdrawn from the study. Each cohort will be then assessed for futility. The results from this IA will be non-binding, unless no signs of efficacy are observed. Safety criteria will also be evaluated to decide on the continuation of the cohorts. During the conduct of the study, after the interim analysis for Cohort A and C and stopping these cohorts for futility, it was considered unlikely that the continuation criteria can be met in Cohort B. Hence it was decided to prematurely stop enrollment after 8 patients in Cohort B.

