7.7.2 ANALYSIS OF SECONDARY EFFICACY ENDPOINTS

Phase 1 (Dose Escalation)

Non-compartmental analysis (NCA) will be conducted using concentration time data of AFM24. In addition, a population PK analysis may be conducted. Separate PK analysis plan(s) will be created as applicable and results will be presented in separate PK report(s). Plots for individual PK concentrations will be generated. PK concentrations will be listed.

ADA results (both screening and confirmatory results as well as titer) will be summarized by visit

CONFIDENTIAL

Page 16 of 22

Statistical Analysis Plan template version 1.0 dated 27-MAR-2019

and change from baseline to worst-post-baseline. Listing of ADA data will be created. The Immunogenicity data will be summarized both for the Safety Set in Phase 1.

Overall response rate (CR + PR) and disease control rate (CR + PR + stable disease [SD]), assessed by Local RECIST v1.1 will be summarized. Best confirmed overall response will be used to define the ORR. Best response is defined as the best observed response (CR>PR>SD>PD) throughout the study. See Table 1 for rules of response confirmation. Summaries will include the count and percentages of different best confirmed overall responses, ORR and DCR for each dose level. The percentages will be based on the total number of patients in the Safety population for a given dose level.

In addition, waterfall plots for percentage change from baseline for sum of longest diameter and swimmer plots showing timing and results of RECIST 1.1 response assessments (both from the central reader and the investigator).

Phase 2 (Dose Extension)

The secondary endpoints for Phase 2a match the ones for the Phase 1. Similar analyses will be performed, but the presentation will be done by Expansion Arm rather than by dose level. Analysis of Adverse Events is described in section 7.8.2.

Waterfall and swimmer plots will also be created, similar to what is described for Phase 1, but additionally color coding the Best confirmed Overall Response.

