7.7.3 ANALYSIS OF EXPLORATORY EFFICACY ENDPOINTS

Phase 1 (Dose Escalation)

Overall response rate (CR + PR) and disease control rate (CR + PR + SD), assessed by: Local iRECIST; Central RECIST v1.1 and Central iRECIST will be summarized.

In addition, Clinical Benefit Rate will be calculated and summarized. It will be defined similarly to DCR, but additionally requiring for SD to last at least 24 weeks.

Duration of Response (DOR) will be defined as (date of first progression or death – date of first response (unconfirmed))/30.4375. Patients without response will be excluded from the analysis. Patients without progression or death will be censored at the date of the last tumor scan.

Progression-Free Survival (PFS) will be defined as (date of first progression – date of first study drug injection)/30.4375. Patients without progression or death will be censored at the date of the last tumor scan.

Overall Survival (OS) will be defined as (date of death – date of first dose)/30.4375. Patients alive at the end of study will be censored on the last date of observation. Separate analyses for DOR and PFS will be created for local and central assessments. Censoring rules for all time-to-event endpoints can be seen in the table below.

Endpoint	Situation	Date	Censored/Event
Overall Survival	A death is recorded	Date of death	Event
Overall Survival	No death is recorded	Latest available observed date	Censored
Duration of Response	A PD is observed	First date of PD	Event
Duration of Response	No PD is observed, but there is a death recorded	Date of death	Event
Duration of Response	Neither PD nor Death are observed	Date of the last Tumor scan	Censored
Duration of Response	New anti-cancer therapy is started before any event is recorded	Date of the new anti-cancer therapy	Censored
Time to Response	A Response is observed	Date of the earliest (unconfirmed) response	Event
Time to Response	No Response is observed	Date of latest tumor assessment	Censored
Progression-Free Survival	A PD is observed	First date of PD	Event
Progression-Free Survival	No PD is observed, but there is a death recorded	Date of death	Event
Progression-Free Survival	Neither PD nor Death are observed	Date of the last Tumor scan	Censored
Progression-Free Survival	New anti-cancer therapy is started before any event is recorded	Date of the new anti-cancer therapy	Censored

PD = progressive disease

CONFIDENTIAL

Page 18 of 22

Statistical Analysis Plan template version 1.0 dated 27-MAR-2019

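### The SAP's confirmation table assigns PD where no PD was scanned, and RECIST v1.1 best response has no stop at first PD; the best-confirmed-response table is wrong as written, and DCR may be

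*SAP*

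**What the plan says.** SAP 7.7.1 makes response by local RECIST v1.1 the Phase 2a primary endpoint and adds: "Best confirmed overall response will be used to define the ORR. The table below summarizes the confirmation rules". The table pairs each scan with the next evaluable one at least 4 weeks later.

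- CR, PR or SD followed by PD gives PD at the earlier visit, without condition.
- CR followed by PR gives PD.
- Rows that end in SD carry a footnote. It asks for another assessment of at least SD, 7 or more weeks after the initial visit (a term the SAP does not define), and continues: "If this criterion is not satisfied, assign PD".
- The last visit receives no confirmed response.

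SAP 7.7.2 adds: "Best response is defined as the best observed response (CR>PR>SD>PD) throughout the study". It summarises best confirmed response, ORR and DCR together, and fixes the denominator: "The percentages will be based on the total number of patients in the Safety population for a given dose level". Phase 2a follows the same approach by expansion arm. SAP 7.7.3 defines DOR as ("date of first progression or death – date of first response (unconfirmed") divided by 30.4375, and dates a PFS event at the first PD.

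Protocol 7.2.11 says: "Partial or complete response needs to be confirmed with repeated assessment at least 4 weeks after the initial assessment". It sets no such requirement for SD. Protocol 4.3 allows treatment beyond first progression: "If treatment is continued after initial progressive disease, a confirmatory scan should be acquired within 4 to 6 weeks". Protocol 9.3.5.1.1.2 defines disease control at months 3, 6 and 9. Protocol Table 2 and the SAP give no months.

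**The concern.** A patient with SD at week 8 and first PD at week 16 is reported with best confirmed response PD, while the SAP's PFS rule counts the same patient as progression-free until week 16. The two outputs contradict each other. The protocol asks for confirmation of CR and PR only. Its interim-analysis wording, that subjects "have completed their first post-baseline assessment and its confirmation", sets when the analysis is done and not how an observed SD is labelled.

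The opposite error comes from the open window. A patient who progresses first and responds later counts as a RECIST v1.1 responder in the primary endpoint, and the DOR formula then gives a negative number. Protocol 9.3.5.1.1.3 instead runs DOR from the response to a progression that follows it.

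At stake are the final best-response table, possibly DCR, and, in rarer patterns, ORR and DOR.

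**Working it through.** There is no stated figure to reproduce, because this is a classification rule. The check applies the SAP table, its footnote and its last-visit rule to scan sequences.

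**Inputs.** Scans on the weekly regimen fall in the last week of cycles 2, 4, 6 and 8, that is weeks 8, 16, 24 and 32 (protocol Table 11 notes). A confirmatory scan after PD comes 4 to 6 weeks later (protocol 4.3). The table has no row that starts with PD; such a visit is taken as PD (assumption).

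| Scans (week) | SAP best confirmed response | Under the fix below |
|---|---|---|
| SD(8) PD(16) | PD | SD |
| PR(8) PD(16) | PD | SD |
| CR(8) PD(16) | PD | SD |
| SD(8) SD(16) PD(24) | SD | SD |
| SD(8) only | none | SD |
| PD(8) only | none | PD |
| SD(8) SD(12), no later scan | PD if the initial visit is the first scan; SD if it is first dose | SD |
| CR(8) PR(12), no later scan | PD | not PD; category to be stated |
| CR(8) PR(16) PR(24) | PR | PR |
| PD(8) PR(12) PR(16) | PR | PD |
| PD(8) SD(12) SD(24) | SD | PD |

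Only a single scan before PD is lost: SD confirmed at the next scheduled scan stays SD. Scans on the 8-week schedule meet the 7-week requirement, so the footnote matters for off-schedule scans.

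**Effect on ORR.** The three rows ending in PD turn one non-response into another, so ORR does not change. ORR rises only through a confirmed response after first PD. It falls only for a CR-PR patient with no other confirmed response.

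**Effect on DCR.** SAP 7.7.2 ties best confirmed response to ORR in words, and to DCR only through the joint summary.

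- If DCR uses best confirmed response, SD-PD counts as no disease control. Each such patient moves DCR by 100/n points: 100/8 = 12.5 (Cohort B as enrolled), 100/11 = 9.1 and 100/15 = 6.7 (interim sizes of A and C; their final enrolment is not stated).
- If DCR uses best observed response, SD-PD counts as SD and the shift from that row is 0.
- In either case, SD recorded after PD can raise DCR, because nothing stops the window.

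**Effect on DOR.** Take PD at week 8 and first PR at the confirmatory scan 4 to 6 weeks later, itself confirmed afterwards. First progression minus first response is -28 to -42 days: -28/30.4375 = -0.92 months and -42/30.4375 = -1.38 months.

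**Effect on the futility stops.** Cohort A may stop at 1 or fewer responses in 11, and Cohort C at 2 or fewer in 15. A cut at first PD can only remove responders, so it cannot lift either cohort above its limit.

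**The case against.** The strongest reply is that the SAP deliberately requires confirmed SD: SD-PD has no second SD, so row and footnote agree, and the protocol does not forbid such a rule. A strict rule is legitimate, but failing confirmation does not turn a recorded SD into progression. The SAP also already has a durability endpoint in Clinical Benefit Rate, which requires SD of at least 24 weeks.

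A second reply is that RECIST v1.1 is cited and governs. A general citation does not override an explicit table that a programmer will follow.

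Three points stand. The use of confirmed response for DCR is implied, not stated. A confirmed response after PD may be rare. DCR is secondary and descriptive, and listings, swimmer plots and PFS will show the underlying scans, although they do not correct the summary tables.

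A reader might infer that DCR is understated by up to 33 points, from the Phase 1 figure of SD in 8 of 24 (protocol 1.6). The documents do not support this. They do not say how many of those 8 had a single SD scan before PD, nor that DCR uses confirmed response. A reader might also infer that the futility stops are unsafe because the table defines the primary endpoint. The rows ending in PD leave ORR unchanged, and the missing stop at PD can only have favoured continuation.

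**Conclusion.** The table is wrong as written and should be corrected before final tables are produced. The best-confirmed-response table is wrong on any reading. The relabelling understates DCR only if DCR rests on best confirmed response: 12.5, 9.1 or 6.7 points per relabelled patient at n = 8, 11 or 15, with the number of such patients unknown. A negative DOR of about -0.92 to -1.38 months is possible under the stated sequence.

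The effect on ORR is confined to two patterns: a confirmed response after PD (raised), and CR-PR with no other confirmed response (lowered). The documents report no patient with either. Whether correcting the CR-PR row would add a responder depends on the category chosen for it.

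The untimed DCR in the SAP is a secondary point. The SAP cites protocol version 9.0, so this may be a version difference, but the two documents need reconciling.

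**What to change.** 1. State in SAP 7.7.2 which response variable defines DCR.
2. Replace the SD confirmation rule with an explicit minimum time from first dose, for example the 7 weeks already in the SAP. Say that this replaces the present requirement for a second assessment of at least SD. A CR, PR or SD visit that meets it and is not confirmed as a response counts as SD, whether the next scan is PD or there is no later scan. Amend the last-visit rule to match; otherwise SD followed by PD would rank above a lone SD scan.
3. Assign PD only when PD was recorded, including as the only scan. Otherwise use not evaluable, kept in the denominator as no disease control. Correct the CR-PR row so that it does not assign PD without a recorded PD.
4. Restrict RECIST v1.1 best response and DOR to assessments up to first PD or new anticancer therapy, and report later responses under the planned iRECIST analysis. This is an analysis cut-off only and does not affect treatment.
5. Reconcile the SAP's untimed DCR with protocol 9.3.5.1.1.2 and Table 2, or list the omission in SAP section 9.

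The cost is SAP wording and reprogramming one derivation on data already collected. Through the cut-off ORR can only fall, and DCR may rise, so the change should be documented before the final tables are run.

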7.7.2 ANALYSIS OF SECONDARY EFFICACY ENDPOINTS

Phase 1 (Dose Escalation)

Non-compartmental analysis (NCA) will be conducted using concentration time data of AFM24. In addition, a population PK analysis may be conducted. Separate PK analysis plan(s) will be created as applicable and results will be presented in separate PK report(s). Plots for individual PK concentrations will be generated. PK concentrations will be listed.

ADA results (both screening and confirmatory results as well as titer) will be summarized by visit

CONFIDENTIAL

Page 16 of 22

Statistical Analysis Plan template version 1.0 dated 27-MAR-2019

and change from baseline to worst-post-baseline. Listing of ADA data will be created. The Immunogenicity data will be summarized both for the Safety Set in Phase 1.

Overall response rate (CR + PR) and disease control rate (CR + PR + stable disease [SD]), assessed by Local RECIST v1.1 will be summarized. Best confirmed overall response will be used to define the ORR. Best response is defined as the best observed response (CR>PR>SD>PD) throughout the study. See Table 1 for rules of response confirmation. Summaries will include the count and percentages of different best confirmed overall responses, ORR and DCR for each dose level. The percentages will be based on the total number of patients in the Safety population for a given dose level.

In addition, waterfall plots for percentage change from baseline for sum of longest diameter and swimmer plots showing timing and results of RECIST 1.1 response assessments (both from the central reader and the investigator).

Phase 2 (Dose Extension)

The secondary endpoints for Phase 2a match the ones for the Phase 1. Similar analyses will be performed, but the presentation will be done by Expansion Arm rather than by dose level. Analysis of Adverse Events is described in section 7.8.2.

Waterfall and swimmer plots will also be created, similar to what is described for Phase 1, but additionally color coding the Best confirmed Overall Response.

